### 1.1 Study Design

This study is a multi-reader, multi-case (MRMC) enriched reader study that will be performed over two years using imaging sets of CESM and breast MRI collected from a screening population.

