### 1.1.1 Case Selection for the Reader Study

Cases to be included will be categorized as negative, biopsy proven benign, and biopsy proven malignant. The total number of cases required for each group can be seen in Figure 3.

Cases needed for reader study	Total # of cases needed for reader study			
Negative/ Biopsy Proven Benign	88			
Biopsy Proven Cancer	44			
Total number of cases	132			
Figure 3. Number of negative, biopsy proven benign, and biopsy proven cancer cases. Given				
the varying proportions identified in FDA approved studies and other MRMC imaging				
evaluations, this ratio of negative/biopsy proven benign to biopsy proven cancer cases was seen				
as acceptable. [1-5]				

Of the 132 imaging sets required for the reader study, 54 were previously acquired through another research study (DF-HCC 14-225) and clinical practice. 4 of these cases were malignant. Cases acquired through DF-HCC 14-225 were incorporated into the Online Medical Record, as specified in the protocol, similar to those cases acquired for clinical practice. We are requesting a waiver of informed consent to include these imaging sets that are a part of the clinical record in the current reader study.

We will prospectively recruit the additional 40 cancers and 38 negative/benign cases necessary for the reader study. These cases will be prospectively recruited from a population of women who are undergoing biopsy in order to maximize the number of cancers identified. This will be discussed in more detail in Section 1.1.2.

Thus, the cases to be collected and used for the reader study will be broken down as demonstrated in Figure 1 of the Schema.

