# 1.1.2 Prospective Image Acquisition:

CESM and MRI images will be prospectively collected to identify additional malignant and benign cases that are required for the reader study. All cases to be prospectively recruited will be selected from a population for whom a breast biopsy has been recommended based on an initial screening study, as illustrated in Figure 2. By performing the imaging prior to the biopsy, this ensures that there are no post-biopsy changes that may bias a radiologist reader during the reader study.

[figure not shown]

Figure 2. Additional images for the reader study will be prospectively recruited. These patients will be recruited prior to receiving breast biopsy (shaded green) based on a finding initially seen on screening mammography.

*Screening and enrollment:* Women will be identified at the time of their diagnostic work-up when a biopsy is recommended. If the participant meets screening requirements, informed consent will be obtained at that time and eligibility tests will be performed. Pregnancy tests will be checked on all premenopausal women and creatinine clearance (to evaluate renal function) will be checked according to the clinical protocol. If the participant meets all eligibility requirements, then she will be enrolled to the study.

To evaluate how CESM works with all types of cancer (both subtle and more obvious), patients will be recruited consecutively from BI-RADS 4A, 4B, 4C, and 5 such that there is an equal distribution among the categories. Patients will continue to be enrolled across all BI-RADS categories until the necessary number of cases with cancer has been acquired.

*Study plan:* Each enrolled participant will receive both a CESM and MRI exam *prior* to the breast biopsy. If the CESM has already been done as part of standard of care within 3 months,

then only the MRI will be performed. If the MRI has already been done as part of the standard of care within 3 months, then only the CESM will be performed. If neither has been performed already, then both exams will be performed prior to the biopsy, to occur within 3 months of each other and the biopsy.

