### 5.1.2 Duration of Follow Up

No additional dedicated research visits are necessary. Participants will be followed for 2 years through review of their chart to determine whether they developed breast cancer. Participants without follow-up or death will be considered lost to follow-up.

The deidentified imaging data may be used for future undefined research. This has been included in the informed consent document.

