# 12.1 Study Design/Endpoints

Exams will be interpreted by 13 radiologist readers. Each reader will score each CESM and MRI exam according to the Breast Imaging-Reporting and Data System (BI-RADS), ranging from 1-5. The score used will correspond to the most suspicious finding in the study. The primary outcome will be whether the exam is benign or malignant. BI-RADS scores 1, 2, and 3 associated with the corresponding categories of negative, benign findings, and probably benign findings will be negative (benign). BI-RADS scores 4 and 5 associated with the corresponding categories of suspicious for malignancy will be positive (malignant).

Positive truth will be determined by histopathology confirming malignant pathology. If a woman has had both a percutaneous breast biopsy and surgical excision, the worst pathology will be considered for analysis.

Negative truth will be considered for all cases categorized as negative or biopsy proven benign. All cases will require two-year follow-up to confirm the absence of malignancy. The follow-up will take the form of any documentation of the woman's health to include the online medical record (OMR) or imaging archival system, or direct communication with her.

At the time of the reader study, there may be cases classified as negative that have not had complete follow-up since their initial CESM and MRI exams. These cases will be reevaluated after the reader study has been completed to confirm whether the cases represent false negatives. This will be accounted for in the subsequent analysis. Given that the false negative rate of MRI is low and approximates 3%, it is unlikely that this will impact the analysis significantly (17).

We will compare the BI-RADS score of CESM and MRI with the final outcome of negative or positive truth to determine the area under the curve for each technology for ROC analysis.

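### Two-year negative truth cannot exist at the only scheduled analysis: essentially all 38 prospective non-cancers fall short at month 24, and no later analysis is dated

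*Combined protocol and SAP*

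**What the plan says.** Section 12.1 counts both negative and biopsy-proven-benign cases as negative truth, and adds: "All cases will require two-year follow-up to confirm the absence of malignancy". For prospective participants, section 5.1.2 provides the means: "Participants will be followed for 2 years through review of their chart to determine whether they developed breast cancer".

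Section 1.1 describes an "enriched reader study that will be performed over two years". The section 9 calendar gives months 0-12 to prospective imaging, 13-15 to categorization, 16 to training, 17-22 to the two reading sessions, and 23-24 to data analysis and report. It shows nothing after month 24.

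Section 1.1.1 gives the case sources: "We will prospectively recruit the additional 40 cancers and 38 negative/benign cases necessary for the reader study". The other 54 sets already exist, and 4 of them are malignant.

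Section 12.1 recognises that at the time of reading "there may be cases classified as negative that have not had complete follow-up since their initial CESM and MRI exams". These cases are to be looked at again once the reader study is over, and the findings taken into account in the analysis that follows. It also says: "We will compare the BI-RADS score of CESM and MRI with the final outcome of negative or positive truth". It then sets the matter aside: "Given that the false negative rate of MRI is low and approximates 3%, it is unlikely that this will impact the analysis significantly".

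Section 13 says that maturity of the outcome data is defined in the sample size section. Section 12.2 contains no such definition.

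**The concern.** The reference standard and the calendar cannot both be met. A woman imaged during the first year completes two years of follow-up during the third, but the only analysis slot closes at the end of the second. The non-inferiority comparison scheduled for months 23-24 would therefore use labels that do not yet meet the plan's own definition of negative truth, and the plan gives no date for the analysis that would.

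A second gap concerns coverage. Section 1.1.3 sorts cases into negative, biopsy-proven benign and biopsy-proven malignant, but the re-evaluation sentence in 12.1 names only those classified as negative. Every prospective woman has a biopsy recommendation (3.1.1). Section 3.2.2 excludes sets where a recommended biopsy was not done and two-year imaging follow-up is missing. Together these rules imply that the prospective non-cancers will be almost entirely biopsy-proven benign. Read literally, the promise could miss nearly all the cases that need it.

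At stake is which result decides non-inferiority, and whether the labels behind it were fixed by a rule set in advance.

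**Working it through.** **Case counts (1.1.1, 1.1.4).** Existing non-cancers: 54 − 4 = 50. All non-cancers: 50 + 38 = 88. Cancers: 4 + 40 = 44. Total: 132. These match the plan.

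**Follow-up at the scheduled analysis.** A woman imaged at month t has T − t months of follow-up at month T and is complete when T − t ≥ 24. With t between 0 and 12:

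- At month 23, follow-up is 11 to 23 months and no case is complete.
- At month 24, follow-up is 12 to 24 months; only a woman imaged on the first day would be complete.
- The last woman is complete at 12 + 24 = month 36.

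So essentially all 38 are short at months 23-24, whatever the accrual pattern: 38/88 = 43%. Imaging dates for the 50 existing non-cancers are not given, so their status is unknown.

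**Effect of relabelling one case.** Move one non-cancer to the cancer group. Let A be the AUC before the move, f the share of the 44 cancers scored above the case, and g the share of the other 87 non-cancers scored below it. Then

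new AUC = (44 × 88 × A − 44f + 87g) / (45 × 87).

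At the plan's A = 0.83:

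- Scored like an average cancer (f = 0.50, g = 0.83): (3213.76 − 22 + 72.21)/3915 = 0.8337, a change of +0.0037.
- Scored like an average non-cancer (f = 0.83, g = 0.50): (3213.76 − 36.52 + 43.5)/3915 = 0.8227, a change of −0.0073.

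If the hidden cancer is seen on both modalities, or missed on both, both AUCs move together and the difference does not change. If it is seen on one only, the difference moves by 0.0037 + 0.0073 = 0.0110, in favour of the modality that saw it. The same calculation gives 0.0084 at A = 0.75 and 0.0134 at A = 0.90. The arithmetic limit for one case, ranked top on one modality and bottom on the other, is (87 + 44)/3915 = 0.033. The margin is 0.05.

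**The 3% figure.** It is a miss rate for MRI among cancers. The quantity needed is the chance that a woman labelled non-cancer has cancer, and then the share of such cancers seen on one modality only. Multiplying 3% by non-cancers (0.03 × 38 = 1.1, or 0.03 × 88 = 2.6) or by known cancers (0.03 × 44 = 1.3) estimates neither.

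**The case against.** The strongest reply is that the plan largely handles this. Section 12.1 anticipates incomplete follow-up, promises re-evaluation and ties the AUC to final truth. Section 5.1.2 commits to two years of chart review, and section 13 lets the end of study wait for mature data. The calendar is a planning table and does not call the months 23-24 analysis final. This stands to the extent that final truth is clearly meant to govern; a reader might infer that the plan ignores the problem, and it does not. But the only slot after the reading sessions is months 23-24, when final truth for these cases cannot exist, and the pointer to a maturity definition leads nowhere.

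Four stronger readings are not supported.

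- A reader might infer that the result would be seriously biased. Under 3.1.1 and 3.2.2 these labels should already rest on benign tissue, and clinical staff read both exams (1.1.2). Only a cancer that was missed at biopsy and seen on one modality matters, and the documents give no frequency for that.
- A reader might infer a range starting at 28.5 cases, using the look-back in 1.1.2 ("If the CESM has already been done as part of standard of care within 3 months", with the same rule for MRI). That gives 38 × 9/12 = 28.5 only if every clock starts three months before enrolment and accrual is uniform. But 12.1 counts from both exams, and 4.1.1 requires registration before study imaging, so at least one exam falls on study. The supportable figure is 38.
- A reader might dismiss the 3% as irrelevant. If it applied here (an assumption), cancers missed by MRI would number about 44 × 0.03/0.97 = 1.4, and 1.4 × 0.011 = 0.015 if all were discordant. It therefore has some bearing on a small effect, but it cannot be the sole reason to set the issue aside.
- A reader might read the re-evaluation sentence as certainly leaving out benign biopsies. The preceding definition of negative truth includes them, so the inclusive reading is natural; the wording is ambiguous.

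**Conclusion.** The point holds as a contradiction between the reference standard and the calendar, together with a missing date for the analysis that meets the standard. Essentially all 38 prospective non-cancers would be unconfirmed at months 23-24, and the last would be confirmed at about month 36. This assumes that imaging runs over months 0-12 as scheduled and that the two years are counted from the CESM and MRI exams; it needs no assumption about accrual pattern.

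The effect on the estimate is probably small: about 0.011 per discordant hidden cancer, in either direction, if the case scores like an average cancer on one modality and an average non-cancer on the other. The number of such cases cannot be derived from the documents. The sponsor should correct this, because the deciding result ought to meet the plan's own truth definition on a date set in advance. It is not a reason to regard the design as unsound.

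**What to change.** In 9.2, 12.1 and 12.2:

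1. State that the deciding non-inferiority analysis uses truth labels locked when the last prospective non-cancer reaches two years from her CESM and MRI exams for this study (about month 36), and add that analysis to the calendar. This also supplies the maturity definition that section 13 refers to.
2. Label any months 23-24 analysis preliminary.
3. State that re-evaluation covers biopsy-proven-benign as well as negative cases.
4. Stop using the 3% rate as the sole reason for expecting little impact.
5. At the final analysis, add a sensitivity analysis that excludes non-cancers still without two-year confirmation.

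The exclusion in item 5 should not be run at month 24. It would remove essentially all 38 prospective non-cancers while 40 of the 44 cancers are prospective, so case source would be confounded with truth.

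Cost: protocol wording, the chart review already planned in 5.1.2, and one re-run with no repeated reads. The downside is that the definitive result comes about 12 months later, although a preliminary report at month 24 remains possible.

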# 12.2 Sample Size, Accrual Rate and Study Duration

Objective 1: To compare the diagnostic accuracy of CESM with breast MRI for detection of breast cancer.

Area under the ROC curve (AUC) of CESM and MRI will be calculated for each of the 13 readers and compared with Delong & Delong (1988)'s method within each reader. The reader average AUC will be calculated for each modality and the difference between the modalities and its associated 95% confidence interval will be calculated using Obuchowski's method.

Objective 2/3: To compare the diagnostic accuracy of CESM with abbreviated MRI for detection of breast cancer.

Area under the ROC curve (AUC) of CESM and abbreviated MRI will be calculated for each of the 10 readers and compared with Delong & Delong (1988)'s method within each reader. The reader average AUC will be calculated for each modality and the difference between the modalities and its associated 95% confidence interval will be calculated using Obuchowski's method.

Objective 4: Descriptive statistics will be used to evaluate patient responses to the survey

*Sample Size Justification:* The analysis aims to test the non-inferiority of CESM when compared to MRI by establishing no loss of value in the ROC AUC. The null hypothesis is HO: (Reader average AUCCESM- reader average AUCMRI) :S -0.05 versus the alternative HA: (reader average AUCCESM-reader average AUCMRI) > -0.05. The test is based on a 2-sided 95% confidence interval on the difference between the reader average AUCs. The ROC power and the sample size calculations are based on the methods of Zhou, Obuchowski and McClish.

Assuming the average AUC of the two modalities is 0.83, the correlation for same reader, different modalities is 0.47, correlation for different reader, same modality is 0.44, correlation for different reader, different modalities is 0.4 and correlation for group of readers, different modalities is 0.8. The interobserver variability is 0.002 and the intraobserver variability is 0.0004. The pooled readings from 13 readers on 44 cancer cases and 88 non-cancer cases will have at least 80% power to reject the null hypothesis that (AUCCESM - AUCMRI) S -0.05 with a 95% 2 sided confidence interval on the difference. The lower end of the confidence interval for the difference (AUCCESM - AUCMRI) must be greater than -0.05 to accept the alternative hypothesis of non-inferiority.

Accrual Targets for Prospective Recruitment					
Ethnic Category	Sex/Gender				
	Fen	nales	11	Males 11	Total
Hispanic or Latino	5				
Not Hispanic or Latino	77			7	
Ethnic Category: Total of all subjects	82	(Al)	+	(Bl) =	(C1
Racial Category					
American Indian or Alaskan Native	0		+	=	
Asian	8		+	7	
Black or African American	8		+	7	
Native Hawaiian or other Pacific Islander	0		+	=	
White	66		+I	11	
Racial Category: Total of all subjects	82	(A2)	_	(B2) =	(C2
	(Al=	= A2)		(Bl=B2)	(C1=C2)

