A. CESM session: - Review and score the low energy images (these images are equal to conventional 2D mammographic images); this will be the MG score

- Then review and score the low energy images combined with the subtraction images (this is the CESM exam); this will be the CESM score.

B. MRI session: - Review and score the abbreviated MRI sequences (these are a subset of the full protocol); this will be the abMRI score. - Then review and score the complete MRI exam; this will be the MRI score.

The order of image presentation per reader is randomized. Half will complete the CESM session first and the other half will complete the MRI session first. Cases will be randomized and counterbalanced to account for learning, experience, and fatigue that occur during reader studies. Readers and study assistants will be blinded to the details of the investigational site, subject history, previous mammography images, and previous clinical results. The radiologist reader will provide a forced BIRADS score of 1,2,3,4a, 4b, 4c, or 5 defined, respectively, as negative, benign findings, probably benign findings, low suspicion for malignancy, moderate suspicion for malignancy, high suspicion for malignancy, and highly suggestive of malignancy associated with probability of malignancy of (0%), (0%), (::=::2%), (>2% to ::=;10%), (>10% to ::=;50%), (>50% to <95%), and (95%), respectively. Each case will also be scored for confidence in diagnosis on a 5-point Likert scale using strongly confident, confident, neutral, not confident, and strongly not confident. This will be the confidence score. Readers will report their interpretations into RedCap database using reader ID numbers and the results will be analyzed anonymously.

The reader study will take place after all the imaging studies have been acquired and reported. Consensus will not be necessary for the reader study. We will be evaluating individual and group ROC curves.

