# **1.4 Third Objectives**

To determine whether CESM is superior to mammography for breast cancer screening

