# 2. BACKGROUND

### 2.1 Study Disease(s)

The limitations of conventional mammography, with its inability to detect breast cancers in dense breast tissue and subsequent reduced sensitivity, are now well-established and have resulted in new legislation in nearly 50% of US states requiring reporting breast tissue density to patients and recommending supplemental imaging screening with ultrasound and MRI. The decreased sensitivity is especially concerning in the intermediate and high-risk groups (6-11). MRI has become the prime alternative in these groups but has its own limitations including increased false positives associated with unnecessary biopsies and anxiety, increased cost, increased time, and decreased availability at many centers (12). Ultrasound is another, less commonly used alternative as it is associated with even more false positives than MRI, is time intensive, and operator dependent.

CESM is a new imaging tool using a dual-energy technique that has been shown in the diagnostic setting to have increased sensitivity for breast cancer detection relative to conventional 2D imaging and equal sensitivity with improved specificity relative to breast MRI. It was FDA approved for diagnostic imaging in 2011. It requires no additional time relative to conventional 2D imaging other than IV line placement and contrast administration and is overall faster than breast MRI. It is less expensive than breast MRI as it is currently being billed as a diagnostic mammogram and is easier to implement into practice than MRI given that it is simply a software upgrade to commonly used mammography equipment and the staff training is minimal.

Given these benefits, CESM may prove to be useful in the screening setting, where traditional imaging tools including 2D imaging, MRI, and ultrasound have shortcomings. This is especially important for those patients who cannot get the more traditional imaging. However, CESM's value in screening has not yet been established. This will be the first reader study that evaluates CESM's role for screening relative to 2D mammography and MRI.

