# **12. STATISTICAL CONSIDERATIONS**

This is a retrospective reader study to compare screening MRI and contrast enhanced spectral mammography for breast cancer screening, for which some cases will be prospectively collected.

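### Section 12.2's Objective 2/3 paragraph specifies only CESM against abbreviated MRI, for 10 readers: as written it does not analyse superiority over mammography, and it conflicts with the 13 readers stated elsewhere

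*Combined protocol and SAP*

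**What the plan says.** Section 1.4 gives the third objective: "To determine whether CESM is superior to mammography for breast cancer screening". Section 2.1 presents the study as the first reader study of CESM's "role for screening relative to 2D mammography and MRI". Sections 1.1.4 and 10.1 have each reader score the low-energy images before the full CESM exam; of that first score they say "this will be the MG score".

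The analysis is in section 12.2, organised by objective. The paragraph covering the third objective is headed "Objective 2/3: To compare the diagnostic accuracy of CESM with abbreviated MRI for detection of breast cancer". Its method sentence begins "Area under the ROC curve (AUC) of CESM and abbreviated MRI will be calculated for each of the 10 readers". It goes on to DeLong comparisons within reader, and a 95% confidence interval for the reader-average difference by Obuchowski's method.

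Elsewhere in section 12, the opening says "This is a retrospective reader study to compare screening MRI and contrast enhanced spectral mammography for breast cancer screening" and section 12.1 says "We will compare the BI-RADS score of CESM and MRI with the final outcome of negative or positive truth". Sections 12.5 and 12.6 only refer back to 12.1 and 12.2. The one success criterion is in the sample-size text: "The lower end of the confidence interval for the difference (AUCCESM - AUCMRI) must be greater than -0.05".

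**The concern.** The label promises an analysis for two objectives, but the text beneath it delivers one. An analyst who followed the paragraph exactly would compare CESM with abbreviated MRI, attach that result to both objectives, and never use the MG score. The third objective is framed as superiority, so it needs a named comparator and a stated basis for the conclusion. Section 12 gives neither. It also leaves open whether the claim would rest on the per-reader DeLong comparisons or on the reader-average interval, a choice best fixed before scores are seen.

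The reader count in the same paragraph is a separate error. It would give the second and third comparisons a different reader sample from the primary one, with no rule for choosing it.

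**Working it through.** **1. Objectives set against section 12.**

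| Objective | Score or data collected | Contrast named in section 12 | Success rule in section 12 |
|---|---|---|---|
| 1 (section 1.2): non-inferior to MRI | MRI score | CESM vs MRI, 13 readers | lower 95% limit above -0.05 |
| 2 (section 1.3): non-inferior to abbreviated MRI | abMRI score | CESM vs abbreviated MRI, 10 readers | not written separately |
| 3 (section 1.4): superior to mammography | MG score | none | none |
| 4 (section 1.5): patient preference | survey | descriptive statistics | none needed |

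Across section 12 the MG score and any superiority criterion each appear 0 times. The word mammography occurs once, as part of the full name of CESM.

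**2. Reader count.** Four statements give 13: section 1.1.4, section 12.1, and in section 12.2 the Objective 1 paragraph and the sample-size text. One gives 10: the Objective 2/3 paragraph. The difference is (13 - 10)/13 = 23%. No 10-reader subset is defined, and section 1.1.4 requires every reader to commit to the whole case set.

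**3. What 10 instead of 13 would do to precision.** This uses Obuchowski's variance for the difference in reader-average AUC:

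Var = (2/J) × [σb²(1 - rb) + σw² + σc²{(1 - r1) + (J - 1)(r2 - r3)}]

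Section 12.2 supplies σb² = 0.002, σw² = 0.0004 (both read as variances), rb = 0.8, r1 = 0.47, r2 = 0.44 and r3 = 0.40. These are stated for CESM vs MRI; using them for the other contrasts is an assumption. The case variance σc² is not given. At AUC 0.83 with 44 cancer and 88 non-cancer cases it is 0.00199 by the binormal approximation and 0.00170 by Hanley-McNeil.

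Binormal value, intraobserver term kept:
- J = 13: (2/13) × [0.0004 + 0.0004 + 0.00199 × (0.53 + 12 × 0.04)] = (2/13) × 0.00281 = 0.000432. The standard error is 0.0208 and the 95% half-width 0.0408.
- J = 10: (2/10) × [0.0008 + 0.00199 × (0.53 + 9 × 0.04)] = 0.2 × 0.00257 = 0.000514. The standard error is 0.0227 and the half-width 0.0445.

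The ratio is 0.0445/0.0408 = 1.09. Over both case variances, with and without the intraobserver term, the half-width is 0.035 to 0.041 with 13 readers and 0.038 to 0.045 with 10, an increase of 8% to 9%.

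**4. Power.** The plan's only power figure, at least 80%, is for CESM vs MRI. With 13 readers, a true difference of 0 and a two-sided 95% interval, the same formula gives 67% to 79% (normal approximation), or 60% to 72% with an F reference. Because the case variance is not stated, this neither confirms nor refutes the 80%, and the present point does not depend on it.

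For CESM vs mammography the plan gives no effect size, correlation or power. Purely as an illustration, I borrow the CESM-vs-MRI inputs (binormal, intraobserver term kept, normal approximation). Superiority power with 13 readers would be 30%, 67%, 82% and 99.8% for true AUC gains of 0.03, 0.05, 0.06 and 0.10. The MG and CESM scores come from one sitting on overlapping images, so the real correlations may differ.

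**The case against.** The best defence is that little is truly missing. The 2/3 label signals that one method was meant for both objectives. Section 1.4 supplies the comparator and the direction, sections 1.1.4 and 10.1 define the MG score, and section 1.1.4 promises individual and group ROC curves. With a 95% interval on a difference, a lower limit above 0 is the conventional meaning of superiority. The 10 looks like a leftover: section 10.1 still gives 150 cases where section 1.1.4 gives 132, and a competent analyst would use 13.

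Much of this stands, and it limits the point. It shows that the intended analysis can be reconstructed. It does not make the paragraph correct: its heading and its method sentence both name abbreviated MRI alone, and the reader count contradicts four other statements.

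The defence also disposes of several stronger readings that a reader might infer:
- That the mammography comparison has been dropped or cannot be done. The objective stands and the score is collected.
- That the -0.05 limit would be used to declare superiority over mammography. It is written for CESM minus MRI and labelled non-inferiority; nothing proposes extending it to mammography.
- That three readers will be discarded or will skip abbreviated MRI. No passage describes this, and the reader commitment in section 1.1.4 points the other way.
- That abbreviated MRI has no margin. Section 1 places complete and abbreviated MRI under one non-inferiority aim, so -0.05 may well be meant for both. This is a matter of wording only.

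**Conclusion.** The point holds: the paragraph is wrong as written, and should be corrected before the reads are analysed. Taken literally, one of the three accuracy objectives gets no analysis, and the reader count is 3 short of 13 (23%). These two findings rest on the text alone. The 8% to 9% widening of the interval depends on the borrowed inputs and assumed case variance, and would arise only if 10 readers were actually used.

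The fault lies in the statistical section, not in the objective or the data. The primary comparison of CESM with complete MRI, with 13 readers and the -0.05 margin, is unaffected. The documents do not show whether the mammography comparison is adequately powered, so no claim is made either way.

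**What to change.** Split the paragraph in section 12.2.

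- **Objective 2:** CESM against abbreviated MRI, by the DeLong and Obuchowski methods already named, for 13 readers. Add a sentence saying whether the -0.05 margin applies here; if another is meant, state and justify it.
- **Objective 3:** reader-average AUC(CESM) minus AUC(MG), by the same methods, for 13 readers. Superiority is concluded if the lower limit of the two-sided 95% confidence interval exceeds 0. Note that the sample size was not calculated for this contrast.

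The cost is a wording change and one further run of the same analysis on scores already planned. No new cases, readers or reads are needed.

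### The stated power of at least 80% does not follow from the inputs in section 12.2; at an assumed true difference of 0 they give about 60–78%

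*Combined protocol and SAP*

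**What the plan says.** Section 12.2 of the combined protocol and SAP states that "The pooled readings from 13 readers on 44 cancer cases and 88 non-cancer cases will have at least 80% power" to reject a deficit of 0.05 or more in reader-average AUC. The aim is described as "establishing no loss of value in the ROC AUC". On the test, it says: "The test is based on a 2-sided 95% confidence interval on the difference between the reader average AUCs". Non-inferiority is accepted if the lower limit lies above -0.05.

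The inputs given are:
- AUC: "Assuming the average AUC of the two modalities is 0.83".
- Case correlations: "the correlation for same reader, different modalities is 0.47, correlation for different reader, same modality is 0.44", and 0.40 for different readers with different modalities.
- Correlation of the reader group across modalities: 0.8.
- Reader terms: "The interobserver variability is 0.002 and the intraobserver variability is 0.0004".

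The calculation is attributed to the methods of Zhou, Obuchowski and McClish. Section 12.2 does not state the assumed true CESM–MRI difference, the case-sampling variance of an AUC, the reference distribution with its degrees of freedom, or whether the two reader terms are variances or standard deviations.

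**The concern.** The listed inputs are nearly the full set that the Obuchowski multi-reader formula needs, so the power claim can be tested. On the most natural reading, the formula does not return 80%.

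This sentence is the plan's justification for 13 readers and for 44 cancer and 88 non-cancer cases. If true power is well below the stated figure, a failed primary comparison could easily arise with equal modalities. Without the assumptions, nobody could tell low power from real inferiority. Type I error, the margin and the decision rule are not affected.

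**Working it through.** **Inputs from section 12.2.** J = 13 readers; 44 cancers and 88 non-cancers; AUC 0.83; r1 = 0.47, r2 = 0.44, r3 = 0.40, rb = 0.8; inter-reader term 0.002; intra-reader term 0.0004; margin 0.05; two-sided 95% interval.

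**Assumptions I had to add.** The true difference is d = 0. The terms 0.002 and 0.0004 are variances (SDs of about 0.045 and 0.02). The case variance Vc and the degrees of freedom are varied.

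**Step 1: what the stated 80% would require.** With a normal reference and d = 0, the standard error may be at most 0.05/(1.960 + 0.842) = 0.0178. It may be at most 0.0172 with Hillis df and 0.0164 with 12 df.

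**Step 2: case variance of one AUC.**
- Obuchowski: A = 1.414 × Φ⁻¹(0.83) = 1.349. Vc = 0.0099·exp(-A²/2)·[(5A² + 8) + (A² + 8)/2]/44 = 0.001993.
- Hanley–McNeil: Q1 = 0.83/1.17 = 0.7094 and Q2 = 2(0.83²)/1.83 = 0.7529. Vc = [0.1411 + 43(0.7094 - 0.6889) + 87(0.7529 - 0.6889)]/3872 = 0.001702.
- Equal-variance binormal: both joint probabilities are 0.7290. Vc = [0.1411 + 130(0.7290 - 0.6889)]/3872 = 0.001383.

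**Step 3: variance of the reader-average difference.**
Var = (2/13)·[0.002(1 - 0.8) + 0.0004 + Vc{(1 - 0.47) + 12(0.44 - 0.40)}] = (2/13)·[0.0008 + 1.01·Vc].
For Hanley–McNeil: (2/13)(0.0008 + 0.001719) = 0.0003875, so SE = 0.0197 and the noncentrality is 0.05/SE = 2.540.

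**Step 4: degrees of freedom.** I used 12 (readers minus 1), a normal reference, and Hillis df = 12·[(M + 13·Vc·0.04)/M]², where M = 0.0008 + 0.49·Vc. For Hanley–McNeil, M = 0.001634 and df = 12·(0.002519/0.001634)² = 28.5.

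**Step 5: power at d = 0.**

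| Case variance | SE | 12 df | Hillis df | Normal |
|---|---|---|---|---|
| Obuchowski, 0.001993 | 0.0208 | 59.8% | 64.3% (30 df) | 67.1% |
| Hanley–McNeil, 0.001702 | 0.0197 | 64.6% | 68.9% (29 df) | 71.9% |
| Equal-variance binormal, 0.001383 | 0.0184 | 70.5% | 74.5% (27 df) | 77.6% |

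All nine values are below 80%. The Obuchowski variance, which is closest to the method the section names, falls furthest short.

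**Step 6: what would bring it to 80%.**
- A smaller case variance: at most 0.000934 (12 df), 0.001098 (Hillis) or 0.001258 (normal). All three standard values are larger.
- A true CESM advantage, in the order 12 df / Hillis / normal: +0.014 / +0.010 / +0.008 (Obuchowski); +0.010 / +0.007 / +0.005 (Hanley–McNeil); +0.006 / +0.003 / +0.002 (binormal).

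In the other direction, a true CESM deficit of 0.005 lowers power to 51–61% (12 df) or 58–69% (normal).

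**The case against.** **The true difference is not stated.** An average AUC of 0.83 does not say that both modalities equal 0.83, and section 2.1 reports "equal sensitivity with improved specificity relative to breast MRI" for CESM in the diagnostic setting. In the most favourable cell, an advantage of only 0.002 closes the gap. It stands that zero is my assumption. But section 12.2 frames the aim as no loss and enters no advantage; if the 80% rests on one, it has to be stated.

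**The reader terms may be counted twice.** The product 0.002 × (1 - 0.8) is exactly 0.0004, so the intra-reader figure may be the same component. Counting it once gives, at 12 df / Hillis / normal, 66/71/74% (Obuchowski), 72/77/79% (Hanley–McNeil) and 79/83/85% (binormal). The documents cannot settle this. Under this reading 80% can be reached at a difference of 0, but only with the smaller case variance; the Obuchowski variance still falls short. Reading both terms as SDs makes them negligible and gives 74–88% (12 df) or 81–93% (normal), but it would mean that readers are practically identical.

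**The score distribution may be favourable.** The non-cancers are mixed: section 1.1.1 says "We will prospectively recruit the additional 40 cancers and 38 negative/benign cases necessary for the reader study", and the other non-cancers come from existing material. Suppose the 38 non-cancers recruited before biopsy score 1.5–2.5 SD higher, or cancer scores have 0.5–0.7 times the non-cancer SD. With all reader terms kept, power is then 73–74% (12 df), 77–78% (Hillis) and 80–81% (normal). On a seven-category scale with assumed cut-points, the highest values found are 75% (12 df) and 82% (normal). So 80% can be reached, but only with a normal reference and a shape the plan does not state.

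**A one-sided 5% test** would give 73–86%, but section 12.2 specifies a two-sided 95% interval.

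Taken together, these points show that the sponsor may hold an unreported input that yields 80%. None shows that the stated inputs yield it.

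**Conclusion.** The concern holds. With both reader terms kept as variances, a true difference of 0 and the stated interval, the shortfall from 80% is about 2 to 20 percentage points, depending on case variance and degrees of freedom. The corresponding risk of missing non-inferiority between truly equal modalities is about 22–40%.

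The conclusion is limited to the claim as written: the figure is not supported by the inputs printed beside it. Because four elements of the calculation are undisclosed, it does not establish that the study is underpowered. Confidence is medium for that reason. The arithmetic itself is firm.

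**What to change.** In section 12.2, recompute the power and replace the present claim with the result. In the same place, state:
- the assumed true AUC difference;
- the case-sampling variance and the model behind it;
- whether 0.002 and 0.0004 are variances, and whether the second is separate from the first;
- the reference distribution and its degrees of freedom.

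If the assumed difference is 0 and both terms are separate variances, the sentence could read: Assuming a true AUC difference of 0 and reader variance components of 0.002 and 0.0004, power is about 60–78%, depending on the case variance and degrees of freedom. The sponsor should then narrow this to a single figure for the variance and degrees of freedom actually used.

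If the 80% rested on a CESM advantage, another reading of the reader terms, or a particular score distribution, state that value and also give the power at a difference of 0.

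Leave the margin, readers, cases and decision rule as they are. The cost is one recalculation and a few lines of text; the only downside is a possibly less favourable stated power.
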